8.6.7 Part A, Visit 5 (~Month 6/Week 24 ± 7 days)—Injection #2

Predose:

1. Query subject or parent: “How have you felt in the last two weeks?” or “How has your child felt in the last two weeks?” Complete [Table 4](#)
2. Vital signs - measured prior to any blood draws
3. AE and concomitant medications assessments
4. Physical Examination—directed
5. Tanner stage
6. Height and weight
7. X-ray of non-dominant hand and wrist
8. Clinical laboratory assessments (hematology, chemistry) as per [Appendix 13.1](#)
9. Urine for urinalysis, performed using dipstick supplied by Sponsor

10. Urine pregnancy test, females only

NOTE: Results must be negative prior to receiving Injection #2

11. Blood samples for basal LH, FSH, testosterone/estradiol concentrations PRIOR to the GnRHa stimulation

12. Blood sample for basal serum leuprolide concentrations PRIOR to the GnRHa stimulation

13. GnRHa stimulation: aqueous leuprolide acetate 20 µg/kg body weight administered SC

14. Blood samples for LH, FSH, testosterone/estradiol concentrations 30 ± 5 minutes AFTER the GnRHa stimulation

Study Drug Administration:

15. Pharmacy - prepare study drug for injection (see Pharmacy Manual for complete instructions)

a. Remove kit from refrigerator, at least 30 minutes prior to planned administration and allow the study drug to reach room temperature

b. Start mixing process with the product kit within ≤ 30 minutes prior to the injection time.

16. Apply topical or local anesthetic (per Investigator discretion) to injection site prior to planned injection time; record medication, dose, route, and time

17. Administer second injection of study drug

Postdose:

18. Final AE assessment prior to subject discharge from clinic

19. Schedule/confirm next visit

8.6.8 Telephone Contact 2 (14 days ± 2 days) Post Injection #2

1. Query Subject or parent: “How have you felt in the last two weeks?” or “How has your child felt in the last two weeks?” Complete [Table 4](#)

8.6.9 Part A, Visit 6 (~Month 9/Week 36 ± 7 days)

1. Query subject or parent “How have you felt in the last two weeks?” or “How has your child felt in the last two weeks?” Complete [Table 4](#)

2. Vital signs - measured prior to any blood draws

3. AE and concomitant medications assessments

4. Physical Examination—directed

5. Tanner stage

6. Height and weight

7. Blood samples for basal LH, FSH, testosterone/estradiol concentrations PRIOR to the GnRHa stimulation test

8. Blood sample for basal serum leuprolide concentrations PRIOR to the GnRHa stimulation test

9. GnRHa stimulation: aqueous leuprolide acetate 20 µg/kg body weight administered SC

10. Blood samples for LH, FSH, testosterone/estradiol concentrations 30 ± 5 minutes AFTER the GnRHa stimulation test

11. Schedule/confirm next visit

8.6.10 Part A, Visit 7 (~Month 11/Week 44 ± 7 days)

NOTE: DO NOT complete Part A, Visit 7, if a decision has been made to conduct Part B extension study. In this case, follow procedures for Part B (Visits 7 to 13) beginning in [Section 8.6.12](#).

1. Query subject or parent: “How have you felt in the last two weeks?” or “How has your child felt in the last two weeks?” Complete [Table 4](#)
2. Vital signs - measured prior to any blood draws
3. Height and weight
4. AE and concomitant medications assessments
5. Blood samples for basal LH, FSH, testosterone/estradiol concentrations
6. Blood sample for basal serum leuprolide concentrations
7. Schedule/confirm next visit

8.6.11 Part A, Visit 8 (~Month 12/Week 48 ± 7 days) End of Treatment or Early Discontinuation

1. Query subject or parent “How have you felt in the last two weeks?” or “How has your child felt in the last two weeks?” Complete [Table 4](#)
2. Vital signs – measured prior to any blood draws
3. AE and concomitant medications
4. Physical Examination-complete
5. Tanner stage
6. Height and weight
7. X-ray of non-dominant hand and wrist
8. Urine pregnancy test, females only
9. Clinical laboratory assessments (hematology, chemistry) as per [Appendix 13.1](#)
10. Urine for urinalysis, performed using dipstick supplied by Sponsor
11. Blood samples for basal LH, FSH, testosterone/estradiol concentrations PRIOR to the GnRHa stimulation test
12. Blood sample for serum leuprolide concentrations PRIOR to the GnRHa stimulation test
13. GnRHa stimulation: aqueous leuprolide acetate 20 µg/kg body weight administered SC
14. Blood samples for LH, FSH, testosterone/estradiol concentrations 30 ± 5 minutes AFTER the GnRHa stimulation test

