8. INVESTIGATIONAL PLAN

8.1 Overall Study Design and Plan

This will be an adaptive design study conducted in two parts as illustrated in [Figure 1](#).

Figure 1 Study Design

Subjects will only receive Injections #3 and #4 if Part B is conducted, based on Part A interim data.

Part A:

This will be a multi-center, open-label, single-arm 12-month study. Pediatric subjects with CPP will receive their first SC injection of the study drug (leuprolide acetate 45 mg for injectable suspension) at the start of the study and the second injection at the Month 6 visit. Subjects will return to the clinic periodically for 12 months from the start of dosing for assessment of efficacy, safety and pharmacokinetics (PK).

An independent DSMB will review the safety of the drug throughout the study.

An interim analysis of LH suppression from the GnRHa stimulation test results will be conducted after approximately 40% of the 40 subjects anticipated to complete 6 months of assessments have data through the Month 6 visit (N = approximately 16). Based on this analysis, if LH concentrations after the GnRHa stimulation test are suppressed to < 4 mIU/mL in < 85% of these subjects, then Part B of the study will be invoked. All subjects still undergoing therapy in the Part A of the study and those yet to enroll in the study, if eligible, will be asked to participate in the Part B extension study for additional dosing at shorter intervals. The progression to Part B extension will be based on evaluations by the DSMB and Sponsor.

Part B Extension:

This part of the study will be conducted based on analysis of interim data from Part A.

NOTE: Because the interim analysis will only provide data from a very small sample size informing the decision to conduct Part B of the study with a 5-month dosing interval, **ALL** new subjects being enrolled into the study will begin with Part A of the study with the first 6-month dosing interval before proceeding to Part B. In this manner, there will be adequate data for comparison of dosing intervals for assessment of optimal efficacy.

If invoked, this will be a multi-center, open-label, single-arm extension following Part A. Only subjects who have received the second injection of the study drug in Part A will be permitted to

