8.1.1 Duration of Study

In Part A, after a 28-day screening period, each subject will participate in the study for 48 weeks. Six months after Injection #1 in Part A, subjects will receive Injection #2 of the study drug. There will be a total of 7 study visits during Part A for a total duration of approximately 12 months.

Part A of the study is expected to take up to 24 months from first subject first visit (FSFV) to last subject last visit (LSLV), if Part B is not conducted.

After the interim analysis, if the DSMB and the Sponsor make the decision to conduct Part B of the study then all currently enrolled eligible subjects and all newly enrolled subjects will receive a total of 4 injections of the study drug. Subjects who have gone beyond the Month 11 visit will not be considered eligible to participate in Part B extension as they would be considered to be out-of-window for Injection #3.

If Part B of the study is invoked, the study length (for both Parts A and B) will be expected to be extended for approximately 10 more months for a total of approximately 34 months from FSFV (Injection #1) to LSLV. With the addition of Part B, commitment of each subject in the study will increase from 12 months to 21 months.

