8.4.1 Schedule of Assessments

Table 1 Schedule of Assessments—Part A

Part A	Screening	Injection #1					Injection #2				End of Treatment ¹	Unscheduled Visit (PI discretion)
Visit Number:		Visit 1	Telephone Contact 1	Visit 2	Visit 3	Visit 4	Visit 5	Telephone Contact 2	Visit 6	Visit 7	Visit 8	
Scheduled Day/Week	Within 28 days	Baseline (Day 0)	Week 2 ± 2 days	Week 4 ± 7 days	Week 12 ± 7 days	Week 20 ± 7 days	Week 24 ± 7 days	Week 26 ± 2 days	Week 36 ± 7 days	Week 44 ± 7 days	Week 48 ± 7 days	
Scheduled Month (approximate)		--		~Month 1	~Month 3	~Month 5	~Month 6		~Month 9	~Month 11	~Month 12	
Written Informed Consent / Assent ²	X											
Inclusion/Exclusion Criteria Review	X	X										
Demographics	X											
Medical History	X											
Complete Physical Examination	X										X	X
Query Subject: How have you felt in the last 2 weeks?			X	X	X	X	X	X	X	X	X	X
Directed Physical Examination		X		X	X		X		X			
Prior or Concomitant Medication Review / Medical Procedures	X	X		X	X	X	X		X	X	X	X
Tanner Stage	X				X		X		X		X	X
Vital Signs ³	X	X		X	X	X	X		X	X	X	X
Weight	X	X		X	X	X	X		X	X	X	X
Height	X	X		X	X	X	X		X	X	X	X
Hand and Wrist X-ray	X						X				X	

¹ If a decision is made to continue into Part B, neither Part A Visit 7 nor the End of Treatment assessment will be completed and subjects will proceed directly to the start of Part B Visit 7 of the study. See the following Schedule of Assessment for Part B.

² Informed Consent/Assent may be signed within 28 days prior to the Baseline visit

³ Vital signs to be measured BEFORE any blood draws

Part A	Screening	Injection #1					Injection #2				End of Treatment ¹	Unscheduled Visit (PI discretion)	
Visit Number:		Visit 1	Telephone Contact 1	Visit 2	Visit 3	Visit 4	Visit 5	Telephone Contact 2	Visit 6	Visit 7	Visit 8		
Scheduled Day/Week	Within 28 days	Baseline (Day 0)	Week 2 ± 2 days	Week 4 ± 7 days	Week 12 ± 7 days	Week 20 ± 7 days	Week 24 ± 7 days	Week 26 ± 2 days	Week 36 ± 7 days	Week 44 ± 7 days	Week 48 ± 7 days		
Scheduled Month (approximate)		--		~Month 1	~Month 3	~Month 5	~Month 6		~Month 9	~Month 11	~Month 12		
Urine Pregnancy Test—females only		X					X				X	X	
Urinalysis	X			X			X				X	X	
Hematology	X			X			X				X	X	
Chemistry	X			X			X				X	X	
Hepatitis B antigen/Hepatitis C antibody	X												
Serum lipids - fasting	X	X											

Schedule of Assessments – Part A continued on next page

Table 1 Schedule of Assessments—Part A (continued)

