Table 2 Blood Sampling Times by Parameter for Visit 1—Part A

Visit Number—Part A Scheduled Day/Month	Visit 1			
	Baseline (Day 0)			
	Time relative to injection			
	≥30 min prior	1 h (±5 min)	4 h (±10 min)	6 h (±15 min)
LH and FSH samples	X	X	X	X
Testosterone/estradiol samples	X	X	X	X
Serum Leuprolide	X	X	X	X

Vital signs to be measured BEFORE any blood draws.

Table 3 Schedule of Assessments—Part B

Part B	Injection #3			Injection #4			End of Treatment	Unscheduled Visit (PI discretion)
Visit Number:	Visit 7	Telephone Contact 3	Visit 8	Visit 9	Telephone Contact 4	Visit 10	Visit 11	
Scheduled Day/Week	Week 44 ± 7 days	Week 46 ±2 days	Week 60 ± 7 days	Week 64 ± 7 days	Week 66 ±2 days	Week 76 ± 7 days	Week 80 ± 7 days	
Scheduled Month (approximate)	~Month 11	~Month 11.5	~Month 15	~Month 16	~Month 16.5	~Month 20	~Month 21	
Written Informed Consent / Assent ⁸	X							
Complete Physical Examination							X	X
Query Subject: How have you felt in the last 2 weeks?	X	X	X	X	X	X	X	X
Directed Physical Examination	X		X	X		X		
Prior or Concomitant Medication Review / Medical Procedures	X		X	X		X	X	X
Tanner Stage	X		X	X		X	X	X
Vital Signs ⁹	X		X	X		X	X	X
Weight	X		X	X		X	X	X
Height	X		X	X		X	X	X
Hand and Wrist X-ray	X			X			X	
Urine Pregnancy Test	X			X			X	X
Urinalysis	X			X			X	X
Hematology	X			X			X	X
Chemistry	X			X			X	X
Serum lipids - fasting	X							
LH and FSH (basal)	X		X	X		X	X	X
Testosterone/Estradiol (basal)	X		X	X		X	X	X
Serum Leuprolide (basal) ¹⁰	X		X	X		X	X	X
GnRHa Stimulation (SC leuprolide acetate)	X			X			X	X
LH and FSH samples 30 min AFTER GnRHa stimulation	X			X			X	X
Testosterone/estradiol samples 30 min AFTER GnRHa stimulation	X			X			X	X
Study drug (leuprolide acetate) SC injection ¹¹	X			X				
Adverse Events Assessment	X		X	X		X	X	X
Schedule/Confirm Next Visit	X		X	X		X		(X)

⁸ Prior to start of Part B extension, parents/guardian(s) and subjects will be asked to sign a new ICF and assent, respectively.

⁹ Vital signs to be measured BEFORE any blood draws

¹⁰ Blood samples for leuprolide serum concentrations must be collected BEFORE the GnRHa stimulation on days the stimulation test is given.

¹¹ Local or topical anesthetic may be used at the discretion of the Investigator prior to study drug administration. Name of the anesthetic used, route, and time of dose must be recorded.

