Baseline	Demographics (continuous)		x				Screening
Baseline	Medical History (categorical)	x					Screening
Baseline	Medical History (descriptive)					x	Screening
Baseline	Meds/Treatments History					x	Screening
Baseline, Safety	Vital Signs		x				Screening, All Visits
Baseline, Safety	Weight		x				Screening, All Visits
Baseline, Efficacy	Height		x				Screening, All Visits
Baseline, Safety	Complete Physical Exam (categorical)	x					Screening, Visit 11
Baseline, Safety	Complete Physical Exam (descriptive)					x	Screening, Visit 11
Safety	Directed Physical Exam (categorical)	x					Visits 1, 2,3,5,6,7,8, 9 10
Safety	Directed Physical Exam (descriptive)					x	Visits 1, 2,3,5,6,7,8, 9 10

 All collected and derived variable values will be in listings. However, this column highlights information that is closely related to information found in an adjacent row of this table; will not be descriptively analyzed; but will be presented in a listing.

 This table assumes that Part B will be invoked. If Part B is not invoked visits will be altered to conform to the *Schedule of Assessments: Part A*.

Variable Class	Variable(s)	Analysis				Listed/Not Analyzed 	Time Points Analyzed (Visits) 
		Categorical Descriptive Analysis	Continuous Descriptive Analysis	Shift Table Analysis	PK Analysis		
Safety	Flare Symptoms	x	x 				Telephone interview weeks 26 & 46, Visits 2-11
Safety	Pregnancy Test	x					Visits 1, 5,7, 9, 11
Safety	Adverse Events	Reported in Listings and Summarized in Tabulations 					Throughout Study
Baseline, Safety	Laboratory Tests 	x	x	x			Screening, All Visits
Baseline	Hepatitis B/C Antibody	x		x			
Baseline, Safety	Serum Lipids (fasting)	x	x				Screening, Visits 1,7
Efficacy	Leuprolide, LH, FSH, Testosterone, Estradiol (basal)		x		x		Screening, All Visits
Efficacy	LH, FSH, Testosterone, Estradiol (GnRHa stimulation) 	x	x				Screening, All Visits
PK	Serum Leuprolide (basal)		x		x		Screening, All Visits
Efficacy	Tanner Staging  and Menses Presence or Change	x	x	x			Screening, Visits 3, 5, 7, 8, 9, 10, 11
Efficacy	All Exploratory Efficacy Endpoints 	x	x				Screening, All Visits

 See Appendix 3: Global Interview Symptom Assessment. Each item will be analyzed separately using categorical descriptive analysis. A count of total number of symptoms will be analyzed using continuous descriptive analysis.

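### If Part B goes ahead, the instruction to drop Part A Visits 7 and 8 has no exception for children who do not enter Part B

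*Protocol*

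**What the plan says.** The note opening protocol section 8.6.10 reads "DO NOT complete Part A, Visit 7, if a decision has been made to conduct Part B extension study" and then sends the site to the Part B procedures. The footnote to Table 1 in protocol section 8.4.1 (footnotes 1 and 4, repeated under SAP Table 1) goes one visit further: "If a decision is made to continue into Part B, neither Part A Visit 7 nor the End of Treatment assessment will be completed". It ends by saying that "subjects will proceed directly to the start of Part B Visit 7 of the study".

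Entry into Part B is not automatic. Section 8.1 says that children still on treatment or yet to enroll, "if eligible, will be asked to participate in the Part B extension study for additional dosing at shorter intervals". Table 3 footnote 8 adds: "Prior to start of Part B extension, parents/guardian(s) and subjects will be asked to sign a new ICF and assent, respectively". Section 8.1.1 sets a cut-off: "Subjects who have gone beyond the Month 11 visit will not be considered eligible to participate in Part B extension".

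The SAP promises follow-up through Part A Visit 8 only in the branch where Part B is not invoked (6.1.1). In the other branch it gives Injections #3 and #4 to all subjects (6.1.2). The time points in SAP Table 5 are written for that branch: "This table assumes that Part B will be invoked".

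**The concern.** The visits are switched off by a decision about the study, while entry to Part B is settled child by child. Two groups fall between the two rules: children whose families decline Part B, and children who have passed the Month 11 visit but not yet reached Month 12 when the decision is taken. Neither group can go to Part B Visit 7, and on a literal reading neither is to have the Part A End of Treatment visit.

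Part A Visit 8 is where the final stimulated LH, hand X-ray, Tanner stage, complete physical examination, safety laboratory tests and pregnancy test are collected. Families who decline may differ from those who continue, so losing these data could leave the Month 12 secondary and safety summaries resting on a selected group. Children who enter Part B are tested 5 months after Injection #2. After the decision, therefore, only children who stay in Part A can supply a stimulated LH about 6 months after a repeat dose, which is relevant to the secondary objective on the dosing interval.

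**Working it through.** The plan states no figure on this point, so the check is mainly a comparison of texts, with some counting.

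**Step 1. Apply the rules to each kind of child** (8.6.10, Table 1 footnotes, 8.1.1, Table 3 footnote 8).

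| Child at the time of the decision | Part A Visit 7 | Part A Visit 8 | Part B Visit 7 | Last scheduled visit |
|---|---|---|---|---|
| Consents to and enters Part B | replaced | replaced | done | Part B Visit 11 |
| Not past the Month 11 visit, family declines | dropped | dropped | not open | Visit 6, Week 36 |
| Past the Month 11 visit, before Month 12 | already done | dropped | not open | Visit 7, Week 44 |
| Past Month 12 | already done | already done | not open | Visit 8, Week 48 |

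The second and third rows are the gap.

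**Step 2. What those children would miss** (protocol Table 1). Injection #2 is at Week 24.
- A decliner is followed for 36 − 24 = 12 weeks after it instead of 48 − 24 = 24. The last stimulated LH and Tanner stage are at Week 36, the last X-ray and safety laboratory tests at Week 24, and the only complete examination is at screening.
- A late child is followed for 44 − 24 = 20 weeks. Visit 7 has basal samples but no stimulation test, X-ray, safety laboratory tests or Tanner stage.

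**Step 3. Whether other provisions fill the gap.**
- Section 8.2.4 asks only for efforts to collect End of Treatment data, and only after premature discontinuation. Section 8.6 ties discontinuation to withdrawal of consent or assent or the list in 8.2.3. Declining Part B is not on that list.
- SAP 12.3 assigns early-termination data to a visit for safety variables only, so efficacy data collected this way have no rule.
- Section 8.5.6.1 keeps SAE reporting open for 6 months after the last Part A dose. That covers SAEs, not laboratory tests, examinations or efficacy.

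**Step 4. What the SAP can accommodate.** In Table 5, vital signs, weight, height, laboratory tests and basal and stimulated hormones are analyzed at all visits, and the Tanner row includes Visit 8. SAP 8.3.1 names stimulated LH at Part A Visit 8. The complete physical examination row (screening and Visit 11) and the pregnancy test row (Visits 1, 5, 7, 9, 11) omit it. Visit 8 also means Month 12 in Part A and Month 15 in Part B, and Table 5 does not separate them.

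**Step 5. How many children.** About 40 are expected to complete 6 months and about 27 to take part in Part B (synopsis): 40 − 27 = 13, and 13/40 = 32.5%. Section 8.1.2 describes the 27 as completing assessments to Month 21, so the 13 can include children who enter Part B and drop out later. It also includes earlier dropouts and any child who finished Month 12 before the decision.

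For the late group, assume uniform accrual of 60 children in 12 months (60/12 = 5 per month) and a delay of 0 to 3 months from the 16th Month 6 test to the decision. Both are assumptions.
- All enrolled children evaluable: interim at 16/5 + 6 = 9.2 months.
- 40 of 60 evaluable: interim at 16/(40/12) + 6 = 10.8 months.
- The decision time T then runs from 9.2 to 13.8 months.
- Children between Month 11 and Month 12 = 5 × [max(0, T − 11) − max(0, T − 12)], which runs from 0 to 5 before any dropout.

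**The case against.** The strongest reply is that the texts were meant for children who go on. The 8.6.10 note redirects to Part B procedures, which only an entrant can follow. The Table 1 footnote speaks of continuing into Part B and of going straight to Part B Visit 7. The synopsis describes the first six visits as coming before entry to Part B. Section 8.6.11 carries no instruction to skip Visit 8, and that visit doubles as the Early Discontinuation visit. This reading is reasonable, and it is why one cannot say that the visits are definitely cancelled for everyone. But neither text states it, and the SAP's wording for the Part B branch leaves no room for a child who does not enter.

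Four further points stand.
- Late children have already had Visit 7; only Visit 8 is at risk for them.
- Most of SAP Table 5 can take Month 12 data. A reader might infer that these results have no place in the SAP, but that is true only of the complete examination and pregnancy test rows.
- The 6-month interval data do not depend on Visit 8 alone. The Month 6 test is untouched, section 8.1 names the first 6-month interval as the basis for comparing intervals, and the objective is qualified by what the data permit.
- The situation arises only if Part B is invoked, and section 6.2 regards inadequate suppression at 6 months as remote.

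**Conclusion.** The gap is real but limited. If Part B is invoked, the instructions as written drop Part A Visits 7 and 8 for families who decline and Visit 8 for the few children between Month 11 and Month 12. The early-discontinuation provisions and SAE reporting recover only part of what is lost. At risk are Month 12 secondary efficacy data and end-of-treatment safety data.

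A reader might infer a threat to the main result. There is none: the Month 6 endpoint is measured before these visits, and the Month 21 endpoint at Part B Visit 11.

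A reader might also take 13 of 40, about a third, as the number losing follow-up. The documents do not support that. They give no refusal rate, and the 13 is at most a rough upper bound that includes dropouts. The 0 to 5 late children rest on the assumed accrual and decision delay.

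**What to change.** Make the condition child-level in protocol section 8.6.10, protocol Table 1 footnotes 1 and 4, and the SAP Table 1 footnote. Part B Visit 7 replaces Part A Visits 7 and 8 only for a child who has consented to and is entering Part B; every other child completes Part A Visits 7 and 8 as scheduled.

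Reconcile SAP 6.1.1 and 6.1.2 with this. SAP 6.1.1 describes those moving to Part B as enrolled children without a second injection, whereas protocol 8.1.1 sets the limit at the Month 11 visit, so the two documents define the remaining group differently. The 8.6.10 note also refers to Part B Visits 7 to 13, although Part B ends at Visit 11.

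In SAP Table 5, label Part A Visit 8 (Month 12) separately from Part B Visit 8 (Month 15), and add the former to the complete physical examination and pregnancy test rows.

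The cost is a wording change in two documents and, for the children concerned, one or two visits already in the Part A schedule.
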